4.2 Exclusion Criteria

4.2.1 Breastfeeding, pregnancy, or plans to become pregnant.

4.2.2 Known allergy/sensitivity or any hypersensitivity to components of the study drugs, or their formulations.

4.2.3 Presence of any confirmed or probable active TB based on criteria listed in the current ACTG Diagnosis Appendix at screening.

4.2.4 History of rifamycin-monoresistant, INH-monoresistant, multi-drug resistant (MDR), or extensively-drug resistant (XDR) TB at any time prior to study entry.

- 4.2.5 Known exposure to rifamycin-monoresistant, INH-monoresistant, MDR- or XDR-TB (e.g., household member of a person with rifamycin-monoresistant, INH-monoresistant, MDR- or XDR-TB) at any time prior to study entry by participant self report or medical records.
- 4.2.6 **History** of peripheral neuropathy Grade ≥ 2 according to the Division of AIDS Table for Grading the Severity of Adult and Pediatric Adverse Events (DAIDS AE Grading Table), Corrected Version 2.1, July 2017, which can be found on the DAIDS RSC website at <https://rsc.niaid.nih.gov/clinical-research-sites/daids-adverse-event-grading-tables>.
- 4.2.7 Active drug or alcohol use or dependence that, in the opinion of the site investigator, would interfere with adherence to study requirements.
- 4.2.8 Acute or serious illness requiring systemic treatment and/or hospitalization within 7 days prior to study entry.
- 4.2.9 Known cirrhosis, a history of decompensated liver disease (ascites, hepatic encephalopathy, or esophageal varices) or current Child Pugh Class B or C hepatic impairment.

NOTE: Refer to [section 6.3.10](#) for Child Pugh scoring and classification table.

- 4.2.10 Initiated, discontinued, or changed doses of drugs that are P-glycoprotein (PGP) inducers, that are P-glycoprotein (PGP) inhibitors, or that are known to have drug interactions with DTG, within 30 days prior to study entry.

NOTE: Refer to the list of prohibited and precautionary medications in [Appendix I](#).

- 4.2.11 Known porphyria at any time prior to study entry.
- 4.2.12 Receipt of any other antiretroviral therapy other than DTG and 2 NRTI within 28 days prior to study entry.
- 4.2.13 Receipt of TAF within 28 days prior to study entry.
- 4.2.14 **Documented resistance that may confer reduced susceptibility to DTG, at any time prior to study entry. This includes the following integrase strand transfer inhibitor (INSTI) mutations: Q148 substitutions, T66A, L74I/M, E138A/K/T, G140S/A/C, Y143R/C/H, E157Q, G163S/E/K/Q, G193E/R, or N155H.**
- 4.2.15 **Clinically suspected INSTI resistance, at any time prior to study entry, as evidenced by prior receipt of INSTI-containing ART, during which time two or more HIV-1 RNA levels of >200 copies/mL were observed after having attained virologic suppression to <200 copies/mL and without known interruption.**

4.2.16 Consumption of more than 3 alcohol beverages on any day within 30 days prior to entry.**4.3 Study Enrollment Procedures**

4.3.1 Prior to implementation of this protocol, and any subsequent full version amendments, each site must have the protocol and the protocol consent form(s) approved, as appropriate, by their local institutional review board (IRB)/ethics committee (EC) and any other applicable regulatory entity (RE). Upon receiving final approval, sites will submit all required protocol registration documents to the DAIDS Protocol Registration Office (DAIDS PRO) at the Regulatory Support Center (RSC). The DAIDS PRO will review the submitted protocol registration packet to ensure that all of the required documents have been received.

Site-specific informed consent forms (ICFs) WILL be reviewed and approved by the DAIDS PRO, and sites will receive an Initial Registration Notification from the DAIDS PRO that indicates successful completion of the protocol registration process. A copy of the Initial Registration Notification should be retained in the site's regulatory files.

Upon receiving final IRB/EC and any other applicable RE approvals for an amendment, sites should implement the amendment immediately. Sites are required to submit an amendment registration packet to the DAIDS PRO at the RSC. The DAIDS PRO will review the submitted protocol registration packet to ensure that all required documents have been received. Site-specific ICF(s) WILL NOT be reviewed or approved by the DAIDS PRO. Sites will receive an Amendment Registration Notification when the DAIDS PRO receives a complete registration packet. A copy of the Amendment Registration Notification should be retained in the site's regulatory files.

For additional information on the protocol registration process and specific documents required for initial and amendment registrations, refer to the current version of the DAIDS Protocol Registration Manual.

Once a candidate for study entry has been identified, details will be carefully discussed with the participant. The participant (or, when necessary, the legal representative if the participant is under guardianship) will be asked to read and sign the approved protocol consent form.

Participants from whom a signed informed consent has been obtained may be screened and enrolled, if they otherwise qualify. An ACTG Screening Checklist must be entered through the DMC Participant Enrollment System.

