- With no gaps in self-reported DTG and NRTI adherence of more than 3 consecutive days in the 28 days prior to study entry
- With no intention to change ART for the duration of the study

NOTE A: Participants who switch from another ART regimen to DTG to meet eligibility requirements for this study will be eligible to enroll as long as the ART is switched at least 28 days prior to study entry.

4.1.8 Chest radiograph (X-ray) or chest computed tomography (CT) scan performed within 30 days prior to study entry without evidence of active TB.

NOTE: An existing chest X-ray or CT scan from within 30 days prior to entry can be used as qualifying chest imaging. If chest imaging will be performed for study evaluation (i.e., Screening), then chest X-ray should be performed. A CT scan will be used only if an existing scan is already available and will not be performed as part of study.

4.1.9 The following laboratory values obtained within 30 days prior to study entry by any US laboratory that has a CLIA certification or its equivalent, or at any network-approved non-US laboratory that operates in accordance with GCLP and participates in appropriate external quality assurance programs.

- Absolute neutrophil count (ANC) >750 cells/mm³
- Hemoglobin ≥ 7.4 g/dL
- Platelet count $\geq 50,000/\text{mm}^3$
- Aspartate aminotransferase (AST) (serum glutamic oxaloacetic transaminase [SGOT]) $<2.5 \times$ the upper limit of normal (ULN)
- Alanine aminotransferase (ALT) (serum glutamic pyruvic transaminase [SGPT]) $<2.5 \times$ ULN
- Total bilirubin $\leq 1.5 \times$ ULN
- **Creatinine $<1.3 \times$ ULN**

4.1.10 For females of reproductive potential, negative serum or urine pregnancy test at Screening within 30 days prior to entry and within 48 hours prior to entry by any US clinic or laboratory that has a CLIA certification or its equivalent, or is using a point of care (POC)/CLIA-waived test, or at any network-approved non-US laboratory or clinic that operates in accordance with GCLP and participates in appropriate external quality assurance programs.

NOTE A: If screening visit occurs within 48 hours prior to entry, only one test will occur prior to entry.

NOTE B: Urine test must have a sensitivity of 15-25 mIU/mL.

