9.2 Premature Study Discontinuation

- Request by the participant to withdraw
- Requirement for prohibited concomitant medications (see section [5.5](#))
- Clinical reasons believed life-threatening by the physician, even if not addressed in the [toxicity section](#) of the protocol
- Failure by the participant to complete either of the intensive PK visits
- Participant repeatedly noncompliant (per investigator's discretion) with study medications as prescribed
- Request of the primary care provider if she or he thinks the study is no longer in the best interest of the participant
- At the discretion of the ACTG, IRB/EC, FDA, NIAID, Office for Human Research Protections (OHRP), other government agencies as part of their duties, investigator, or industry supporter

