APPENDIX I: PROHIBITED AND PRECAUTIONARY MEDICATIONS

Division of AIDS
AIDS CLINICAL TRIALS GROUP (ACTG)
For Protocol A5372

The prohibited and precautionary medications with dolutegravir (DTG), rifapentine (RPT), and isoniazid (INH) are listed below.

I. Prohibited Medications

- Phenytoin
- Phosphenytoin
- Lamotrigine
- Perampanel
- Phenobarbital
- Primidone
- Carbemazepine
- Oxcarbazepine
- Eslicarbazepine
- Felbamate
- St. John's wort
- Dofetilide
- Azole antifungals including fluconazole, itraconazole, ketoconazole and posaconazole (topical formulations are acceptable as they do not achieve systemic concentration)
- Enzalutamide
- Mitotane
- Other rifamycin antibiotics including rifabutin and rifampicin
- Tenofovir alafenamide (TAF)
- Other antiretroviral drugs except DTG and 2 NRTI
- Protease inhibitors (HIV or HCV)

II. Precautionary Medications

- Antacids – follow product labeling for instructions on separation with DTG
- Buffered Medications – follow product labeling for instructions on separation with DTG
- Divalent cations (e.g., calcium or iron supplements) – follow product labeling for instructions on separation with DTG
- Ethinyl estradiol/norgestimate
- Metformin
- Methadone
- Multivitamin – follow product labeling for instructions on separation with DTG
- Omeprazole
- Prucalopride
- Sucralfate
- Topiramate

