4.2.2 Secondary PK Analysis Population

Secondary PK Analysis Population (separately defined for Arm 1 and Arm 2 participants): The secondary PK analysis population consists of those participants who met all study entry criteria and for whom at least one DTG concentration is available where the dates, times and dose amounts of DTG doses in the three days leading up to the intensive PK sampling visit. Concentrations from all participants, not just evaluable participants, will be used (limited to those concentration for which the dates, times and dose amounts of DTG in the days leading up to the PK visit are available).

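### Exclusion 4.2.10 bars only recent changes in interacting drugs, so a stable user of most Appendix I prohibited drugs can be enrolled and give a Day 0 profile before the prohibition applies.

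*Protocol*

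**What the plan says.** Protocol 4.2.10 excludes a candidate who "Initiated, discontinued, or changed doses of drugs that are P-glycoprotein (PGP) inducers", of P-glycoprotein inhibitors, "or that are known to have drug interactions with DTG, within 30 days prior to study entry". Its note adds only this pointer to Appendix I: "Refer to the list of prohibited and precautionary medications in".

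Two neighbouring criteria are written differently and turn on use. 4.2.12 excludes "Receipt of any other antiretroviral therapy other than DTG and 2 NRTI within 28 days prior to study entry", and 4.2.13 does the same for TAF.

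Appendix I, section I, lists drugs prohibited with DTG, RPT or INH. They include ten anticonvulsants, St. John's wort, other rifamycins and, for example, "Azole antifungals including fluconazole, itraconazole, ketoconazole and posaconazole" (topical forms excepted). Section 5.5.2 makes this list the on-study prohibition. Section 9.2 gives "Requirement for prohibited concomitant medications" as a reason for premature study discontinuation.

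On the data side, SAP 4.2.2 defines the secondary PK population as people who satisfied the entry criteria and have at least one DTG concentration with known recent dosing. It states: "Concentrations from all participants, not just evaluable participants, will be used". SAP 4.5.2 builds the Arm 2 opening model on the Arm 1 members of that population.

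On timing, 4.1.7 NOTE A says that people who switch to DTG are "eligible to enroll as long as the ART is switched at least 28 days prior to study entry".

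**The concern.** The entry rule and the on-study rule do not match. Someone on a long-standing, unchanged dose of a listed anticonvulsant or systemic azole, with a suppressed viral load, can meet every line of 4.1 and 4.2. Once enrolled, the same person is taking a drug that the protocol prohibits, and needing that drug is a listed reason to leave the study.

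This matters statistically because each participant is their own control (Protocol 10.1). Day 0 is meant to describe once-daily DTG before 1HP. A Day 0 profile taken under an interacting drug does not. It can affect the analysis in two ways: through the Arm 1 population model used to simulate once-daily dosing for the Arm 2 decision, and through the denominator of the GMR if the person completes both PK visits.

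**Working it through.** The main check is a comparison of sections.

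1. **Entry criteria.** Of 4.1.1 to 4.1.11 and 4.2.1 to 4.2.16, the only criteria that exclude for receiving a named class of concomitant drug are 4.2.12 and 4.2.13. 4.2.10 excludes for a start, stop or dose change.
2. **Coverage of the list.** Appendix I, section I, has 19 entries. TAF is covered by 4.2.13 and other antiretrovirals by 4.2.12. HIV protease inhibitors also fall under 4.2.12, although the HCV part of that entry is not named there. This leaves 19 − 3 = 16 entries that are caught only if recently changed. Even then, 4.2.10 speaks of PGP drugs and DTG interactions, while Appendix I also covers RPT and INH, so the two scopes differ.
3. **Sequence.** Under 4.3.3, people who meet the criteria are registered. Under 6.2.2, Day 0 sampling is completed before study treatment starts on Day 1. The drug-interaction review in 5.5 is triggered when a concomitant drug or study agent is started or its dose changed. For a stable user that trigger comes with the first dose of study treatment, after the Day 0 profile.
4. **Stopping the drug before entry.** This does not resolve the matter, because a discontinuation within 30 days is itself excluded by 4.2.10 for drugs in its scope.
5. **Where the Day 0 data go.** If the person leaves, Protocol 10.4 keeps dropouts' data in the analysis, and SAP 4.2.2 with 4.5.2 takes an Arm 1 profile into the opening model. If the person completes, SAP 4.2.1 has no condition on prohibited drugs, so the pair enters the GMR. SAP 4.8.2 plans no sensitivity analysis.

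**Illustrative size for the GMR.** The plan has no figure to reproduce. Assume that a listed drug had lowered the Day 0 trough to 30–50% of its undisturbed value and was stopped after Day 0. The person's Day 28/Day 0 ratio is then inflated by r = 1/0.50 = 2.0 to 1/0.30 = 3.33. With k such people among n = 32, the GMR is multiplied by exp(k × ln r / 32).

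| k | r = 2.0 | r = 3.33 |
|---|---|---|
| 1 | exp(0.693/32) = 1.022 | exp(1.204/32) = 1.038 |
| 2 | exp(1.386/32) = 1.044 | exp(2.408/32) = 1.078 |

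The 30–50% range and the values of k are assumptions. The Protocol describes an effect on DTG for rifamycins (2.1.1) but not for the other listed drugs. For a drug that raised DTG, the distortion would run the other way. The effect on the simulated Arm 2 trough cannot be calculated from the documents.

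**Windows.** 4.1.7 NOTE A accepts a switch made at least 28 days before entry. 4.2.10 looks back 30 days, so someone who stopped an earlier antiretroviral 28 to 30 days before entry is eligible under the note. The same person is excluded under 4.2.10 if that drug is in its scope.

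**The case against.** The strongest reply is that a sensible site would not enrol such a person. The note to 4.2.10 sends the screener to the prohibited list, 6.3.3 requires a 30-day prescription history, and 9.2 makes the conflict plain. This does make the event less likely. But the note refers to prohibited and precautionary drugs alike and does not say that use excludes. None of these provisions is an entry criterion, and the authors wrote use-based exclusions in 4.2.12 and 4.2.13 where they wanted them.

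Four stronger readings are tempting but not supported:

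- **A reader might infer that each case uses one of the four spare places (36 − 32) in an arm.** The Schema and Protocol 10.4 say that participants without the required PK are replaced and not counted towards the 36. The cost is a replacement enrolment.
- **A reader might infer that the dosing verdict is compromised.** The comparison with 158 ng/mL in Protocol 10.6 concerns C_trough, which 10.2.1.2 defines at Day 28 only, so a distorted Day 0 profile does not enter it. A distorted Day 28 trough would need the prohibited drug to continue despite 5.5.2 and 9.2.
- **A reader might take the GMR shift as decisive.** SAP 6.5 gives the equivalence limits no numerical values, so there is no stated threshold to cross.
- **A reader might infer a broad conflict between the 28- and 30-day windows.** Exclusions are cumulative: 4.2.12 and 4.2.13 merely fail to exclude after 28 days. Only NOTE A, which affirms eligibility, is in tension with 4.2.10, over about two days and only for antiretrovirals within its scope.

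**Conclusion.** The gap is real and follows from the wording alone. Most drugs prohibited on study are not barred at entry when the dose is stable, and the prohibition applies only after the control profile has been taken. The consequence is a Day 0 profile that does not represent DTG without interacting drugs. An Arm 1 profile of this kind is retained for the Arm 2 opening model, and in either arm it is used in the GMR if the person stays evaluable. Otherwise the person has to be replaced.

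The number of such people is unknown. Under the stated assumptions, one or two among 32 move the GMR by a factor of 1.02 to 1.08, which is probably small. No decision is shown to change. The case for acting rests on an internal conflict that is cheap to remove, not on a demonstrated bias.

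**What to change.** Reconcile 4.2.10 with 5.5.2, Appendix I section I and 9.2, so that the existing prohibited list is applied as an entry criterion and checked before the Day 0 profile. The sponsor should set the look-back window. Keep the change-only rule for interacting drugs that are allowed on study. As a minor item, reconcile the 30-day window in 4.2.10 with the 28-day window in 4.1.7 NOTE A.

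The cost is one criterion and an aligned window at the next amendment. A few candidates will be screened out before enrolment instead of being lost after it. Most of the information is already collected, since 6.3.3 requires prescription drugs for the 30 days before entry. A listed product taken without prescription, such as St. John's wort, would need to be asked about.

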4.3.2 Protocol Activation

Prior to enrollment, sites must complete the Protocol Activation Checklist found on the ACTG Member website. This checklist must be approved prior to any screening of participants for enrollment.

4.3.3 Participant Registration

For participants from whom informed consent has been obtained, but who are deemed ineligible or who do not enroll into the initial protocol step, an ACTG Screening Failure Results form must be completed and keyed into the database.

Participants who meet the enrollment criteria will be registered to the study according to standard ACTG DMC procedures.

4.4 Co-enrollment Guidelines

- US sites are encouraged to co-enroll participants in A5128, “Plan for Obtaining Informed Consent to Use Stored Human Biological Materials (HBM) for Currently Unspecified Analyses.” Co-enrollment in A5128 does not require permission from the A5372 protocol chairs.
- Non-US sites are encouraged to co-enroll participants in A5243, “Plan for Obtaining Human Biological Samples at Non-U.S. Clinical Research Sites for Currently Unspecified Genetic Analyses.” Co-enrollment in A5243 does not require permission from the A5372 protocol chairs.
- For specific questions and approval for co-enrollment in other studies, sites should contact the team via e-mail as described in the [Study Management section](#).

5.0 STUDY TREATMENT

Study treatment is defined as dolutegravir (DTG), rifapentine (RPT), and isoniazid (INH).

5.1 Regimens and Duration

Arm 1

- DTG 50 mg orally BID (~12 hours apart)
 - 1st dose: DTG 50 mg each morning from non-study ARV supply
 - 2nd dose: DTG 50 mg each evening from study supply
- 1HP: INH 300 mg + RPT 600 mg orally each morning for 4 weeks

Arm 2 (upon opening)

- DTG 50 mg orally each morning from non-study ARV supply
- 1HP: INH 300 mg + RPT 600 mg orally each morning for 4 weeks

All participants must be on stable once-daily DTG-based ART with 2 nucleoside reverse transcriptase inhibitors (NRTI).

All participants must receive pyridoxine (vitamin B6) 25 or 50 mg with each dose of INH based on the current local, national, or international dosing guidelines. Pyridoxine is not provided by the study.

5.2 Administration and Dispensing

Dolutegravir (DTG) will be administered orally as 50 mg either QD or BID. As RPT and INH will be given with food, the DTG dose when aligned with 1HP administration will be given with food as well. DTG doses not aligned with 1HP doses may be given with or without food with exception of DTG doses taken on Day 0 and Day 28, which should be taken with food. Separate each DTG 50 mg dose by 12 hours when giving BID. In Arm 1, 1HP should be taken with the first daily dose of DTG.

Isoniazid (INH) will be administered orally as 300 mg QD. INH may be taken with food and at the same time as rifapentine. The 300 mg tablets must not be divided or crushed.

Rifapentine (RPT) will be administered orally as 600 mg QD with food.

To align with the PK sample collections, participants should be on morning dosing regimen for the duration of the study (except the 2nd dose DTG in Arm 1), including at least 3 days prior to Day 0 intensive PK. The dose on the morning of PK sampling day will be an observed dose. Thus, participants will need to hold the dose until the clinic visit.

1HP medications will be provided for Day 1 to Day 28. DTG 50 mg tablets will be dispensed to participants in Arm 1 of the study for the second daily dose of DTG. Participants will continue 2 NRTI plus one dose DTG 50 mg daily from their own supply while on the study treatment regimen in both Arm 1 and Arm 2 (Day 1 to Day 28). Participants will have up to 6 weeks from enrollment to complete 4 weeks of 1HP treatment. Following 1HP, participants will continue antiretroviral therapy prescribed by their routine HIV care provider.

The 1HP treatment is ideally taken once daily for 28 consecutive days. If doses are interrupted, participants are allowed up to 42 days to complete the 1HP therapy. For Arm 1 participants, BID dosing of DTG should continue for the entire 1HP treatment, up to 42 days. Additional doses of DTG for Arm 1 may be dispensed as required, either in intact bottles or dispensed into prescription bottles. For Arm 2 participants, daily DTG and NRTIs should continue from their own supply for the entire 1HP treatment.

5.3 Study Product Formulation

Dolutegravir (DTG): 50 mg tablets. Store at 25°C (77°F) with excursions between 15° and 30°C (59°-86°F) permitted (see USP Controlled Room Temperature).

Isoniazid (INH): 300 mg tablets. Store below 30°C (86°F) and in the original container.

Rifapentine (RPT): 150 mg tablets. Store at 25°C (77°F) with excursions between 15° and 30°C (59°-86°F) permitted (see USP Controlled Room Temperature).

5.4 Pharmacy: Product Supply, Distribution, and Accountability

5.4.1 Study Product Acquisition/Distribution

DTG 50 mg (Tivicay) is supplied by ViiV Healthcare Ltd.

INH is purchased from Macleods Pharmaceuticals Ltd.

Rifapentine (Priftin[®]) will be manufactured by Sanofi and supplied through the study with funding support from the ACTG.

DTG (where applicable), INH, and RPT will be made available through the NIAID Clinical Research Products Management Center (CRPMC). The site pharmacist should obtain the study products for this protocol by following the instructions in the manual *Pharmacy Guidelines and Instructions for DAIDS Clinical Trials Networks*.

Pyridoxine (vitamin B6) will not be provided through the study and should be obtained locally by the site.

Any study product not provided by the study must comply with the NIAID (DAIDS) policy that outlines the process for authorizing the use of study products not marketed in the US in NIAID (DAIDS)-supported and/or –sponsored clinical trials. This policy is available on the NIAID (DAIDS) website at:
<https://www.niaid.nih.gov/sites/default/files/NonFDAapprovedProducts.pdf>.

